3.5. Part 2 Secondary Endpoint(s)

- *Time-to-event endpoints: eg, DoR, PFS, OS.*
- *PK parameters of PF-07265028 (ie, $C_{ss,max}$ and $C_{ss,min}$) and sasanlimab (ie, C_{min} in selected cycles).*
- *For food effect subset only: PK parameters of PF-07265028 (including C_{max} , T_{max} , AUC_{tau} , AUC_{last}) under fasted and fed conditions.*
- *Incidence and titers of ADA and NAb against sasanlimab.*

CCI

090177e198da3551\Approved\Approved On: 16-Dec-2021 03:17 (GMT)

CCI

3.7. Baseline Variables

Baseline characteristics will be collected according to Schedule of Activities as specified in the protocol. No baseline variable will be used for stratification or as covariates for the primary statistical analysis. Unless otherwise specified, the baseline value is defined as the value collected at the time closest to, but prior to, starting the study intervention administration in the first cycle.

4. ANALYSIS SETS (POPULATIONS FOR ANALYSIS)

Data for all participants will be assessed to determine if participants meet the criteria for inclusion in each analysis population.

Table 1. Analysis Sets

Participant Analysis Set	Description
Full Analysis Set (FAS)	All enrolled participants who have been assigned to treatment. Participants are analyzed according to the treatment they were assigned .
Safety Analysis Set (SAS)	All enrolled participants who receive at least 1 dose of study treatment. Unless otherwise specified the safety analysis set will be the default analysis set used for all analyses.

090177e198da3551\Approved\Approved On: 16-Dec-2021 03:17 (GMT)

Table 1. Analysis Sets

Participant Analysis Set	Description
Per-Protocol Analysis Set (DLT-Evaluable Set)	All enrolled participants who had at least 1 dose of study treatment and either experienced DLT or do not have major protocol deviations during the DLT observation period.
mITT Population	All enrolled participants who have received at least 1 dose of study medication; have a baseline assessment and at least 1 post-baseline assessment.
PK Parameter Set	All enrolled participants treated who do not have protocol deviations influencing PK assessment, and have sufficient information to estimate at least 1 of the PK parameters of interest.
PK Concentration Set	All enrolled participants who are treated and have at least 1 analyte concentration above the lower limit of quantitation.
Response Evaluable Set	All enrolled participants who received at least 1 dose of study treatment and had adequate baseline disease assessment. Participants who discontinued early or died will be included.
Pharmacodynamic/ Biomarker Analysis Sets	The Pharmacodynamic/Biomarker analysis population is defined as all enrolled participants with at least 1 of the Pharmacodynamic/Biomarkers evaluated at pre- and/or postdose.
Immunogenicity Analysis Set	The immunogenicity analysis set is a subset of the safety analysis set and includes participants who have at least 1 analyzed sasanlimab ADA/NAb sample.

5. GENERAL METHODOLOGY AND CONVENTIONS

5.1. Hypotheses and Decision Rules

There will be no formal hypothesis testing in this study.

Decision Rules for Part 1 Dose Escalation:

The dose escalation in the Part 1 of the study will be guided by a Bayesian analysis of Cycle 1 DLT data for PF-07265028. A traditional 2-parameter BLRM will be used to model the DLT relationship of PF-07265028 monotherapy, and a more complex BLRM model specifically designed for combinations will be used to model the dose toxicity relationship of PF-07265028 given in combination with sasanlimab. Using DLT data at all tested dose levels and pre specified prior distribution of model parameters, the posterior distribution for probability of having a DLT will be calculated for all dose levels.

After each cohort of participants, the posterior distribution for the risk of DLT for new participants at different doses of interest for PF-07265028 monotherapy and combination therapy will be evaluated. The posterior distributions will be summarized to provide the posterior probability that the risk of DLT lies within the following intervals:

- *Underdosing: [0, 0.16]*
- *Targeted dosing: [0.16, 0.33]*
- *Overdosing: [0.33, 1]*

Dosing decisions are guided by the escalation with overdose control principle.¹ A dose may only be used for newly enrolled participants if the risk of excessive toxicity at that dose is less than 25%.

Weakly informative prior distributions based on preclinical/expert opinion information will be chosen for the logistic parameters, see Protocol Appendix 11 Section 10.11.

A MAP approach may be used to derive the prior distribution for model parameters used in Part 1B based on the data collected in Part 1A and historical DLT data on sasanlimab as monotherapy. The MAP prior for the logistic model parameters for this study is the conditional distribution of the parameters given the historical data. MAP priors are derived from hierarchical models, which take into account possible differences between the studies. A full description of the application of the MAP approach to derive the prior distributions of the model parameters is given in Technical Supplement.

The starting dose is 25 mg PF-07265028. For this dose the prior risk of overdosing is 7.1%, which satisfies the EWOC criterion. A full assessment of the prior risk to participants is given in Protocol Appendix 11 Section 10.11.

The number of participants in Part 1 dose escalation of the trial may be approximately 60. The trial for Part 1A and Part 1B will be stopped when the following criteria are met:

At least 6 participants have been treated at the MTD/RDE.

The dose \tilde{d} satisfies one of the following conditions:

- *The probability of target toxicity at dose \tilde{d} exceeds 50%, ie, $\Pr(0.16 \leq \pi_{\tilde{d}} < 0.33) \geq 50\%$.*
- *A minimum of 12 participants have been treated for Part 1A, or a minimum of 9 participants have been treated for Part 1B.*

To mitigate the risk of dichotomizing and misclassifying DLTs, a sensitivity analysis that uses weighted DLT/AE data (in equivocal cases) into the BLRM model estimation will also be performed. If all the investigators and the sponsor agree on the equivocal DLT/AE data, the DLT weighting approach could be the primary dose escalation method.

Decision Rules for Part 2 Dose Expansion:

The main objective is to evaluate the RDE for PF-07265028 in combination with sasanlimab for safety and preliminary efficacy. Summary statistics will be provided for safety and efficacy endpoints, without formal hypothesis testing.

Sample Size Consideration:

A maximum sample size of 240 participants will be enrolled in the study including approximately 60 participants in Part 1 dose escalation and up to 180 participants in Part 2 dose expansion.

Approximately 60 participants will be enrolled in the Part 1 dose escalation portion of the study, including approximately 30 participants in Part 1A and 30 participants in Part 1B. The actual number of participants enrolled in Part 1 will depend on the tolerability of PF-07265028 as monotherapy and in combination with sasanlimab and the number of dose levels required to identify the MTD/MAD or RDE.

In Part 2A for combination therapy (4 cohorts in total), up to 40 participants will be enrolled for each expansion cohort. If the expansion cohort as monotherapy is explored based on emerging clinical, safety, PK, or PD data, then 20 additional participants will be enrolled for Part 2B. The sample size is based on practical consideration that the stated sample size will provide sufficient evidence of preliminary efficacy of PF-07265028 alone and in combination with sasanlimab. For an expansion cohort in Part 2A, for example, if minimal or no anti tumor activity is observed in the first 15 participants in each cohort, the enrollment for that cohort may be discontinued.

CCI

5.2. General Methods

Whilst every effort has been made to pre-specify all analyses in this statistical analysis plan, CCI, the analyses and the reasons for them will be detailed in the clinical study report (CSR).

Unless otherwise specified, the baseline value is defined as the value collected at the time closest to, but prior to, the start of study drug administration in the first cycle. All data will be categorized based on the scheduled visit at which it was collected. These visit designators are predefined values that appear as part of the visit tab in the case report form (CRF).

The data will be summarized by dose level, defined by the initial dose of the study intervention administered to participants. If a dose level has more than 1 cohort, data from these cohorts will be combined. DLT rates at the study dose levels will be presented via mean and medians and a Bayesian credible interval based on the posterior density from the full probability model. This information will also be used for the dose level review meetings (DLRM) to guide the dose escalation.

For Part 1A and Part 1B, when there are multiple dose levels, in addition to data presentation by dose level, the overall summary combining all dose levels may also be presented.

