In monotherapy, starting dose for PF-07265028 is 25 mg administered orally QD on a continuous basis. BLRM is used for dose finding until reaching MTD. Continuous BID dosing may be explored. The potential switch from continuous QD dosing to BID dosing would be based on emerging PK, PD and safety data. This switch may be needed if data demonstrate that PF-07265028 has a shorter than expected half-life with inadequate PK/PD coverage through QD dosing, or there are AEs related to C_{max} which might be mitigated by a lower dose given BID.

PF-07265028 will initially be administered under the empty stomach condition. The effect of food on PF-07265028 PK will be evaluated in at least 6 participants (food effect subset) at a dose level not exceeding the PF-07265028 MTD and RDE, either as a cohort in Part 1A or in 1 of the Part 2 cohorts. If emerging PK data from the food effect assessment suggest the effect of food on PF-07265028 PK is not clinically meaningful, participants may be instructed to take PF-07265028 without regards to food. In addition, the study has included a plan to assess the effect of food intake on tolerability and safety, if treatment-related Grade ≥ 2 GI toxicity is observed in $\geq 30\%$ participants with a minimum of 6 participants enrolled in total across all dose levels. The dose of PF-07265028 for the evaluation of food effect on tolerability is expected to yield a steady-state AUC and C_{max} not exceeding the AUC and C_{max} of PF-07265028 at the MTD administered under the empty stomach condition. If food intake could allow participants to tolerate the same or higher systemic exposure of PF-07265028 compared to the empty stomach condition, subsequent parts of the study will continue with the dosing regimen of PF-07265028 administered with food.

In combination therapy, sasanlimab 300 mg SC Q4W will be administered at the clinic together with oral administration of PF-07265028.

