6.1.1. Administration

6.1.1.1. PF-07265028

Participants will swallow PF-07265028 tablets whole with at least 8 ounces (240 mL) of water, and will not manipulate or chew the study intervention prior to swallowing. PF-07265028 will initially be administered QD by mouth for all cohorts on a continuous basis. Participants who are unable to swallow whole tablets may dissolve their dose in oral syringe(s) as outlined in the IP manual to allow for suspension administration either orally or via an NG tube. If supported by emerging data, BID continuous regimen may be considered. A cycle is defined as 28 days, regardless of missed doses or dose delays.

Participants will take PF-07265028 at approximately the same time within each dosing interval (ie, ± 3 hours of nominal time). On site visit days, participants will take the drug at the site after performing predose assessment. On other days, participants will be instructed to self-administer the drug at home. A dosing diary will be given to each participant to support at home dosing. The participants will be requested to note the date and time of each dose, food consumption status at the time of drug administration.

If a participant misses a dose at the scheduled time, the participant can still take the dose within 4 hours of the scheduled time. If the participant missed taking a dose after 4 hours of the scheduled time, or day of treatment, they must be instructed not to “make it up” but resume subsequent doses as prescribed. This dose will be considered as a missed dose. In addition, if a participant vomits any time after taking a dose, they should not “make it up” but to resume subsequent doses as prescribed. Lastly, if a participant inadvertently takes 1 extra dose during a day, the participant should not take the next dose of PF-07265028.

Food Requirements (Except for the Food-Effect Subset or Cohorts Evaluating Food Intake on Tolerability)

Participants will take PF-07265028 orally with at least 8 oz (240 mL) of water on an empty stomach. No food or liquids other than water will be consumed for 2 hours before and 2 hour following each dose throughout the study).

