These empty stomach requirements may be removed (via a letter to the investigators) if results from the food-effect subset indicate there is no clinically meaningful effect of food on the PK of PF-07265028. If food is demonstrated to improve tolerability for participants included in the cohorts where PF-07265028 is administered with food, participants in all cohorts may be instructed to take PF-07265028 with a meal.

Food Requirements for the Food-Effect Subset

Participants enrolled in the food-effect subset will take PF-07265028 under the fasted and fed conditions on Cycle 1 Day 15 and Day 16, respectively, and under empty stomach condition for the remaining portion of the study.

Fasted condition: Following an overnight fast of at least 6 hours, PF-07265028 will be administered and continue fasting for an additional 2 hours postdose. Water will be allowed ad libitum except for 1 hour before and 1 hour after drug administration.

Fed condition: Following an overnight fast of at least 6 hours, participants will start a high-fat/high-calorie breakfast in the clinical sites within 30 minutes prior to and finish breakfast before administration of PF-07265028. No additional food will be allowed until at least 2 hours postdose. Water will be allowed ad libitum except for 1 hour before and 1 hour after drug administration. The breakfast will be high-fat (approximately 50% of total caloric content of the meal) high-calorie (approximately 800-1000 calories with 150, 250, and 500-600 calories from protein, carbohydrate, and fat, respectively) meal.

Food Requirements for Cohorts Evaluating the Effect of Food on PF-07265028 Tolerability

Each dose of PF-07265028 will be administered with a meal and with approximately 8 ounces (240 mL) of water.

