6.1.1. Dose-Limiting Toxicities (DLTs)

- Analysis set: Per protocol analysis set.
- Analysis methodology:

For the purpose of dose escalation, the DLT observation period will be during the first cycle (28 days after the start of study treatment), or DLT window, in each participant. According to the design, cohort sizes are planned to be approximately 3, but it is required to have at least 2 DLT-evaluable patients in the dosing cohorts. The participants who cross over from Part 1A monotherapy to Part 1B combination therapy will be excluded from the DLT assessment in Part 1B.

Whether an adverse event a participant experienced during the DLT window is determined as a DLT or not is based on the DLT definitions provided in Section 4.3.3 of the protocol. A DLT yes/no checkbox will be provided in the case report form, where the investigator provides his/her judgement if an event is a DLT or not. However, the final determination will be reached between the investigators and the sponsor during the dose level review meeting (DLRM). These final decisions will be documented.

The DLT events will be summarized by dose level. A listing of the DLTs events will also be provided in which the participant primary diagnosis (malignancy), dose level the participant was enrolled to, DLT event start day and stop day relative to the cycle 1 day 1 dose date, the DLT event term, NCI CTCAE grade, relatedness to the investigational product (PF-07265028), or sasanlimab (Part 1B), outcome of the event, along with other variables deemed important, will be included.

- Missing data: All enrolled participants in Part 1 should have an indicator variable derived to be either 1 (yes) or 0 (no) based on the DLT definitions and participant's

safety data during the DLT observation window. If a participant fails to have a value on the indicator variable because the participant being non-DLT-evaluable, the participant may be replaced.

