6.1.2. Adverse Events

- Analysis set: Safety analysis set.
- Analysis methodology:

Adverse Events (AEs) will be graded by the investigator according to NCI CTCAE version 5.0 and coded using the MedDRA. The focus of AE summaries will be on Treatment Emergent Adverse Events (TEAEs). TEAE is defined as any adverse event that occurs during the on-treatment period, on or after the first dose of study treatment, and before the last dose of study treatment + 28 days, or the start of any other anti-cancer therapy, whichever is earlier. AEs that occurs after the on-treatment period may still be recorded in the clinical database and will be included in the AE listings, but will not be included in the AE summaries.

The number and percentage of participants who experienced any AE, serious AE (SAE), treatment related AE (i.e. related to any of the study treatment PF-07265028, or sasanlimab), and treatment related SAE will be summarized by system organ class (SOC) and preferred terms (PT) according to worst toxicity grades. The summaries will present AEs for the entire on-treatment period and for the various parts of the study (by dose level for Parts 1A and 1B, by arm for Part 2), and will not be presented by treatment cycle. In the summary tables for Parts 1A and 1B, a “Total” column, summarizing data across all dose levels, will be presented. Additionally summaries of adverse events leading to death and premature withdrawal from study treatment will be provided.

- Missing data: If AE start or stop date is missing, imputation will be performed according to [Section 5.3](#). The imputed dates will be used to determine whether the AE is to be included in the TEAE summary. The missing AE start or stop dates will be listed as is in AE listings. When the CTCAE grade is missing for an AE, the AE will be excluded from the CTCAE grade summary table.

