6.2.1. Pharmacokinetic Analysis

6.2.1.1. PK Parameter Analysis

- Analysis set: PK Parameter Set
- Analysis methodology:

In Part 1, following single dose administration of PF-07265028, plasma PK parameters including the C_{max} , T_{max} , AUC_{last} , $AUC_{tau,ss}$ and if data permit, AUC_{inf} , CL/F , V_z/F , and $t_{1/2}$ will be estimated. Following multiple doses of PF-07265028, steady-state PK parameters including $C_{max,ss}$, $T_{max,ss}$, $AUC_{last,ss}$, $AUC_{tau,ss}$, $C_{min,ss}$, CL_{ss}/F , and if data permit, V_{ss}/F , $t_{1/2}$, and R_{ac} ($AUC_{tau,ss}/AUC_{tau,ss}$) will be estimated. In Part 2 participants Not in food-effect subset, following multiple doses of PF-07265028, C_{min} will be reported. In participants in food-effect subset, steady-state PK parameters including $C_{max,ss}$, $T_{max,ss}$, $AUC_{last,ss}$, $AUC_{tau,ss}$, $C_{min,ss}$, CL_{ss}/F under fasted and fed conditions will be estimated. In Part 1 and Part 2, following multiple doses of sasanlimab, C_{min} in selected cycles will be reported.

The single-dose and steady-state PK parameters will be summarized descriptively (n , mean, standard deviation, CV, median, minimum, maximum, geometric mean and its associated CV) by dose, cycle, and day.

Trough concentrations (C_{min}) will be plotted for each cohort using a box-and-whisker plot by cycle and day within cycle in order to assess the attainment of steady state. Dose normalized C_{max} , AUC_{last} , AUC_{tau} (at steady state) will be plotted against dose (using a logarithmic scale) by cycle and day. These plots will include individual participant values and the geometric means for each dose. These plots will be used to help understand the relationship between the PK parameters and dose.

For the evaluation of the food effect, PF-07265028 plasma concentration-time data will be compared on days taken under fasted (Reference) and fed conditions (Test). PK parameters ($C_{max,ss}$, $T_{max,ss}$, $AUC_{last,ss}$, $AUC_{tau,ss}$) of PF-07265028 given under fasted and fed conditions will be summarized descriptively. Natural log transformed AUC and C_{max} values will be analyzed using an analysis of variance model and treatment as fixed effects. Estimates of the mean differences (Fed-Fasted) and

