6.2.1.2. PK Concentration Analysis

- Analysis set: PK Concentration Set
- Analysis methodology:

Presentations for plasma PF-07265028 and serum sasanlimab will include:

- A listing of all concentrations sorted by dose, subject ID, cycle, and nominal time post-dose. The listing of concentrations will include the actual sample collection times, and the time of dosing. Deviations from the nominal time will be given in a separate listing.
- A summary of concentrations by dose, cycle, and nominal time post-dose, where the set of statistics will include n, mean, median, standard deviation, coefficient of variation (cv), minimum, maximum and the number of concentrations above the lower limit of quantification.
- Plots of median concentrations against nominal time post-dose by dose (based on the summary of concentrations by dose, cycle, and time post-dose), with all doses presented on the same plot. Two plots will be generated, so that the concentrations can be presented on linear and logarithmic scales.
- Plots of geometric mean concentrations against nominal time post-dose by dose (based on the summary of concentrations by dose, cycle, and time post-dose), with all doses presented on the same plot. Two plots will be generated, so that the concentrations can be presented on linear and logarithmic scales.
- Plots of individual concentrations against actual time post-dose (separate plots for each dose). Two plots per dose will be generated, so that the concentrations can be presented on linear and logarithmic scales.
- Plots of concentration against actual time post-dose by subject (separate line for each dose). Two plots per subject will be generated, so that the concentrations can be presented on linear and logarithmic scales.

For summary statistics and median plots by sampling time, the nominal PK sampling time will be used. For individual subject plots by time, the actual PK sampling time will be used. Exclusions or separate summaries for dose modifications and concomitant medications may be considered in data summaries.

- Missing data: missing concentration and BLQ values will be handled according to [Section 5.3.3](#).

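### Where a fed tolerability cohort shares a dose with a fasted cohort, the SAP's pooling rule merges them in the planned safety tables and the by-dose PK tables

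*SAP*

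**What the plan says.** **The decision.** Under Protocol 4.1, once at least 6 participants are enrolled across dose levels, treatment-related GI toxicity of Grade 2 or worse in at least 30% of them triggers an assessment of how food affects tolerability and safety. The dose for that assessment is limited by exposure: expected steady-state AUC and Cmax may not exceed those at the empty-stomach MTD. Nothing says the dose must match, or must differ from, one already given fasted. If food lets participants "tolerate the same or higher systemic exposure of PF-07265028 compared to the empty stomach condition", later parts go on with food.

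**The cohorts.** Protocol 6.1.1.1 treats these cohorts as distinct from the food-effect PK subset. The heading of its empty-stomach rules carries the exception "Except for the Food-Effect Subset or Cohorts Evaluating Food Intake on Tolerability". For the tolerability cohorts, "Each dose of PF-07265028 will be administered with a meal and with approximately 8 ounces (240 mL) of water". The food-effect subset has a single fed dose, on Cycle 1 Day 16, and returns to empty-stomach dosing.

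**The grouping.** SAP 5.2 defines dose level by the initial dose and then states, with no exception, "If a dose level has more than 1 cohort, data from these cohorts will be combined". The Part 1 outputs use that grouping:
- SAP 6.1.1: "The DLT events will be summarized by dose level".
- SAP 6.1.2 and 6.1.3: adverse events and laboratory abnormalities by dose level.
- SAP 6.2.1.1: PK parameters summarised descriptively ("geometric mean and its associated CV) by dose, cycle, and day").
- SAP 6.2.1.2: concentrations by dose, cycle and nominal time.

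**The concern.** The protocol names a regimen choice and the contrast on which it turns: tolerability with food against tolerability on an empty stomach, judged relative to exposure. A natural way to isolate food is to give the fed cohort a dose already studied fasted. In that case the SAP's grouping rule removes the contrast from the tables that would report it. Fed and fasted participants share one DLT row, one adverse-event column, one laboratory column and one by-dose PK summary.

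At stake is whether the planned and reported summaries can support a choice of regimen that later parts will follow. If they cannot, the comparison has to be built ad hoc after the data are seen.

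**Working it through.** The plan gives no figure on this point, so there is none to reproduce. The check sets the sections side by side and then illustrates the size with assumed counts.

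**Step 1: can the two regimens share a dose level?** Protocol 4.1 caps the fed dose by AUC and Cmax at the fasted MTD. A dose already given fasted meets that cap as long as food does not push expected exposure above it. SAP 5.2 identifies a dose level by initial dose only. A shared dose level is therefore possible but not certain.

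**Step 2: does any planned table separate them?** In the visible text, SAP 6.1.1 to 6.1.3 do not mention food. SAP 6.7 plans no subset analyses. SAP 6.2.1.2 leaves some room for splitting PK summaries: "Exclusions or separate summaries for dose modifications and concomitant medications may be considered in data summaries". Food condition is not among the reasons named. The one fed-versus-fasted analysis, in SAP 6.2.1.1, is of PK and has no safety endpoint.

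**Step 3: what the merged safety cell hides.** Assume 6 fasted and 6 fed participants at one dose, and 4 of the 12 with a treatment-related GI event of Grade 2 or worse. The merged cell reads 4/12 = 33% (Clopper-Pearson 95% CI 9.9% to 65.1%). With *a* events among the fasted, the fed have 4 − *a*, and the difference, fasted minus fed, is (2*a* − 4)/6:

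| Fasted | Fed | Fasted minus fed |
|---|---|---|
| 4/6 (67%) | 0/6 (0%) | +67 points |
| 3/6 (50%) | 1/6 (17%) | +33 points |
| 2/6 (33%) | 2/6 (33%) | 0 |
| 1/6 (17%) | 3/6 (50%) | −33 points |

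Every row gives the same merged cell, so it is compatible with food helping, doing nothing or harming. The result does not depend on the assumed size. At about 3 per cohort, the planned size in SAP 6.1.1, a merged 2/6 fits 2/3 v 0/3, 1/3 v 1/3 or 0/3 v 2/3.

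**Step 4: what the merged by-dose PK row shows.** Assume equal group sizes and a fed/fasted AUC ratio *r*. The merged geometric mean is √*r* times the fasted value and 1/√*r* times the fed value:

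| Assumed *r* | Relative to fasted | Relative to fed |
|---|---|---|
| 0.7 | 0.84 | 1.20 |
| 1.5 | 1.22 | 0.82 |
| 2.0 | 1.41 | 0.71 |

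That row describes neither regimen. This applies only to the tables grouped by dose.

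**Step 5: how much separate columns would show.** Exact 95% intervals are 22% to 96% for 4/6, 12% to 88% for 3/6, 4% to 78% for 2/6, 0.4% to 64% for 1/6 and 0% to 46% for 0/6. Separate columns make the contrast visible but do not make it precise.

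**The case against.** The strongest reply has four parts.

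- **Exposure is largely covered elsewhere.** Under Protocol 4.1.3, the same GI trigger moves the food-effect PK assessment into Part 1A. A within-participant fed/fasted comparison, with geometric mean ratios and 90% CIs, is then available. SAP 6.2.1.1 plots troughs for each cohort, Protocol 9.3.3.1.1 summarises concentrations by dosing cohort, and SAP 6.2.1.2 plans individual listings and plots. This stands, and it confines the PK point to the by-dose tables. The food-effect comparison rests on one high-fat meal, so it does not describe continuous dosing with meals.
- **The decision-makers see more than the tables.** Protocol 4.2.2 has a safety review team looking at individual and summary data, and SAP 6.1.1 has DLTs settled and documented at dose level review meetings. This also stands. A reader might infer that the regimen would be chosen blind to food condition; the documents do not support that.
- **The harm is conditional and can be repaired.** It needs the 30% trigger, a fed cohort and a shared dose. The study tests no hypotheses, and SAP section 1 foresees amendment. This bears on severity. It does not remove the rule, which as written has no exception.
- **Absence is judged from redacted documents.** Some exploratory text is blacked out and the Technical Supplement is not available. The claim is therefore limited to the visible DLT, adverse-event, laboratory and PK sections.

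**Conclusion.** The point holds in a limited form and is minor. If the trigger opens a fed tolerability cohort at a nominal dose also given fasted, SAP 5.2 merges the two regimens in the planned DLT, adverse-event and laboratory summaries and in the by-dose PK tables. Those tables then cannot show the tolerability contrast that Protocol 4.1 uses. The group sizes, event counts and food ratios above are assumptions; the documents supply none of them.

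Some wider readings are tempting but not supported:
- **Once- and twice-daily cohorts would also be pooled.** SAP 5.2 speaks of the initial dose. The Table 7 footnote on total daily dose is an escalation rule, so the merge follows only if one replaces the SAP's wording.
- **The same fault arises when the fed dose differs.** The fed cohort then has its own column; what is missing is a label, and any contrast would mix food with dose.
- **The adverse-event total column is at fault.** A total across dose levels is meant to include every cohort.
- **Escalation would be distorted.** The model in Protocol 10.11.1 has dose as its only covariate, but the documents do not say how fed cohorts would enter it, and any effect depends on invented data. Take 0/3 DLTs at each of 25, 50 and 80 mg and 0/6 fed at 125 mg. With 3/6 fasted at 125 mg, the overdose probability at 200 mg is 0.462 on fasted data and 0.201 pooled, either side of the 25% limit. With 2/6 fasted it is 0.220 and 0.077, and both pass. No weight is placed on this.

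**What to change.** In SAP 5.2, combine cohorts at a dose level only when the food condition is also the same. Where fed and fasted cohorts share a dose, show these in separate fed and fasted columns:
- DLTs
- treatment-related GI adverse events of Grade 2 or worse
- laboratory abnormalities
- steady-state AUC and Cmax, because Protocol 4.1 judges tolerability against exposure.

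Label the comparison descriptive and non-randomised.

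The cost is a sentence or two of SAP text and one grouping variable. The dosing diary in Protocol 6.1.1.1 already records food status at each dose. The downside is smaller denominators and wider intervals in each column.
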